## Progression-free survival

PFS is defined as the time from the start date of study drug to the date of the first radiologically documented PD or death due to any cause.

If a patient has not progressed or is not known to have died at the date of analysis cut-off or has received any further anticancer therapy, PFS will be censored at the date of the last adequate tumor evaluation before the cut-off date or before the start of the new anticancer therapy date, whichever is earlier. Clinical deterioration will not be considered as a qualifying event for progression. Refer to [Table 2-1](#) for censoring and event date options and outcomes for PFS.

In particular, PFS will be censored at the last adequate tumor assessment: **if** one of the following occurs: absence of event; the event occurred after a new anticancer therapy is given; the event occurred after two or more missing tumor assessments (see [Section 4.6.1](#)). See also [Section 4.6.1](#) describing the special case of a missing baseline tumor assessment.

PFS will be described in tabular and graphical format using Kaplan-Meier methods as described for DOR, including estimated median (in months) with 95% CI, 25th and 75th percentiles and Kaplan-Meier estimated probabilities with corresponding 95% CIs at several time points (including at least 4, 8, 12, 15 and 18 months). Censoring reasons will also be summarized.

These analyses will be performed separately based on investigator assessment and based on BIRC assessment.

## Overall survival

OS is defined as the time from the start date of study drug to the date of death due to any cause. If the patient is alive at the date of the analysis cut-off or lost to follow-up, then OS will be censored at the last contact date prior to data cutoff date (see [Section 4.3](#) for further details on derivation of last contact date).

OS will be described in tabular and graphical format using Kaplan-Meier methods as described for DOR, including estimated median (in months) with 95% CI, 25th and 75th

percentiles and Kaplan-Meier estimated probabilities with corresponding 95% CIs at several time points (including at least 4, 8, 12, 18 and 24 months). Censoring reasons will also be summarized.

### Duration of Follow-up and Gap Analyses

The duration of treatment period will be reported:

Treatment period = Last patient last date of treatment - First patient start date of treatment + 1

In addition, descriptive statistics including quartiles will be tabulated for the duration of follow-up in the study:

- Duration between start date of study drug and cut-off date = (Cut-off date - Start date of study drug + 1).
- Follow-up time for PFS/OS = (Date of event or censoring - Start date of study drug + 1).

All summaries will be reported in months (see [Section 4.4](#)). The calculations for PFS will be based on the investigator and BIRC assessments. Date of censoring is the same as the one defined for the PFS and OS analyses.

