4.3 Definition of end of the study

There will be no interim analysis of efficacy. The primary analysis will occur once all patients have completed at least 6 cycles of treatment with LDK378 or have discontinued earlier. At this time, the primary clinical study report (CSR) will be produced. Following the primary analysis time point, the study will remain open. Patients still being followed on the study will continue as per the schedule of assessments.

Following the cut-off date for the analysis reported in the primary CSR, the study will remain open. Ongoing patients will continue to receive study treatment and be followed as per the schedule of assessments, as long as patients derive benefit from LDK378. The end of study defined as the earliest occurrence of one of the following:

- At least 75% of patients have died or all patients discontinued from the study.
- Other clinical studies (e.g. roll-over protocol or other) or patient support programs become available that can continue to provide LDK378 in this patient population and all patients ongoing are eligible to be transferred to them.
- At the end of the study, every effort will be made to continue provision of study treatment outside this study through an alternative setting to patients who in the opinion of the Investigator are still deriving clinical benefit.

The final analysis will occur at the end of the study. All available data from all patients up to this cut-off date will be analyzed and summarized in a final CSR.

4.4 .Early study termination

The study can be terminated at any time for any reason by Novartis. Should this occur, the patient should be seen as soon as possible and the same assessments as for a prematurely withdrawn patient as described in [Section 7](#) should be performed. The investigator may be informed of additional procedures to be followed in order to ensure that adequate consideration is given to the protection of the patient's interests. The investigator will be responsible for informing IRBs and/or ECs of the early termination of the trial.

5 Population

[figure not shown]

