### 2.1 Data analysis

Data will be analyzed by Novartis Oncology Biostatistics and programming personnel according to the data analysis section 10 of the LDK378A2203 protocol. Important information is given in the following sections and details are provided, as applicable, in Section 4 from which Appendix 16.1.9 of the CSR will be extracted.

SAS® version 9.4 (or later version if available at time of database lock) will be used in all analyses.

Data from all patients who signed informed consent in centers that participate in this study will be used in the analysis; due to expected small size of enrollment at individual centers, no center effect will be assessed. Each analysis will use all data in the database up to the analysis cutoff date, determined prior to database lock.

As described in Section 1.1 this study has a Simon two-stage design. If the study stops at the end of Stage 1 (see Section 2.11), the data available will be summarized in an abbreviated CSR. Otherwise, the analysis cut-off date for the primary analysis of study data will be established once all patients have either completed at least six treatment cycles, i.e., 168 days (1 cycle = 28 days), or discontinued study drug earlier. The data will be summarized in the primary CSR. Following the primary analysis time point, the study will remain open. Patients still being followed on the study will continue as per the schedule of assessments.

The analysis cutoff date for the final analysis of study data will be 22-Jan-2018 corresponding to last patient last visit date.

[Section 4.1](#) provides further details regarding data to be included in the analyses.

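### SAP 2.8.1 labels the PFS/OS analysis time itself as follow-up time, so when most patients have events its median understates how long they were observable

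*SAP*

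**What the plan says.** Under Duration of Follow-up and Gap Analyses, SAP 2.8.1 states that "descriptive statistics including quartiles will be tabulated for the duration of follow-up in the study". It lists two durations:

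- The first is potential follow-up: "Duration between start date of study drug and cut-off date = (Cut-off date - Start date of study drug + 1").
- The second is "Follow-up time for PFS/OS = (Date of event or censoring - Start date of study drug + 1"), with the note that "Date of censoring is the same as the one defined for the PFS and OS analyses". For PFS it is computed for both investigator and BIRC assessments.

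The same SAP section defines PFS as the "time from the start date of study drug to the date of the first radiologically documented PD or death due to any cause" and states that "OS is defined as the time from the start date of study drug to the date of death due to any cause". Both are analysed by Kaplan-Meier, with medians, quartiles and a summary of censoring reasons.

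On timing, SAP 2.1 states: "The analysis cutoff date for the final analysis of study data will be 22-Jan-2018 corresponding to last patient last visit date". One of the end-of-study triggers in Protocol 4.3 is "At least 75% of patients have died or all patients discontinued from the study".

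Neither document plans a follow-up estimate that treats events as censored.

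**The concern.** A follow-up figure should tell the reader how long patients could have been observed for the endpoint, and so how mature the curve is. The second duration does not do this, because it stops at the event. A patient who progresses at month 2 was fully observed for PFS, yet is tabulated with 2 months of follow-up. With everything else equal, a less effective drug would appear to have had shorter follow-up.

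The item also adds little. The PFS and OS paragraphs already report Kaplan-Meier medians and quartiles of the same times, whereas this item gives raw quartiles that ignore censoring.

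At stake is how the study report is read. In a single-arm trial, readers judge the PFS and OS curves partly by the quoted follow-up. A figure close to the median PFS, presented as PFS follow-up, would make the data look less mature than they are.

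**Working it through.** **Plan's own figure.** The documents give no follow-up figure to reproduce. The design table (SAP Table 2-3) does reproduce by exact two-stage binomial (success 0.0487 at 35% and 0.9000 at 50%, against the stated 0.049 and 0.900), but nothing here depends on it.

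**Step 1: compare the definitions.** Let T be the time from start of drug to the event and C the time to the endpoint's censoring date.

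- PFS or OS analysis time: min(T, C), by the PFS and OS paragraphs.
- Follow-up time for PFS/OS: event or censoring date, minus start, plus 1 day, with the same censoring date. This is again min(T, C).

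Apart from the one-day counting convention, the two are identical for every patient at any event rate.

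**Step 2: why the median collapses onto the endpoint.** With T and C independent, P(min(T, C) > x) = P(T > x) × P(C > x). Suppose there is no dropout and every patient's potential follow-up exceeds the endpoint median m. Then at x = m the product is 0.5 × 1 = 0.5, so the median of the SAP variable is m itself.

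For example, assume 12 months' uniform accrual and cut-off 50 months after the first patient, so C is uniform on 38 to 50 with median 44.0.

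- Exponential PFS with median 16: the SAP median is 16.0 months.
- Exponential OS with median 50: solve exp(−0.693x/50) × (50 − x)/12 = 0.5. At x = 39.6 this is 0.578 × 0.867 = 0.50, so the SAP median is 39.6 months.

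**Step 3: range by simulation.** There were 124 patients (the number treated, Protocol Amendment 4 rationale), 1,000 runs and exponential event times. Assumptions not in the documents: potential follow-up uniform on 40–55 or 24–36 months, dropout 0% or 10% per year, endpoint medians 6.7 to 51 months. The low end, 6.7, is the phase I median PFS in pretreated patients (Protocol 1.3), a different population. Entries are averages over runs, in months; Kaplan-Meier medians are averaged over runs in which they were reached.

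| Potential follow-up | Dropout per year | Events | SAP follow-up median | Endpoint Kaplan-Meier median | Reverse Kaplan-Meier median | Median start to cut-off |
|---|---|---|---|---|---|---|
| 40–55 | 0% | 99% | 6.7 | 6.8 | 45.3 | 47.5 |
| 40–55 | 0% | 95% | 11.1 | 11.2 | 47.6 | 47.5 |
| 40–55 | 0% | 84% | 18.0 | 18.3 | 47.6 | 47.5 |
| 40–55 | 0% | 74% | 24.2 | 24.5 | 47.6 | 47.5 |
| 40–55 | 0% | 60% | 35.8 | 36.6 | 47.5 | 47.5 |
| 40–55 | 0% | 48% | 41.7 | 47.0 | 47.5 | 47.5 |
| 40–55 | 10% | 92% | 6.2 | 6.8 | 42.7 | 47.5 |
| 40–55 | 10% | 64% | 18.5 | 24.1 | 44.1 | 47.5 |
| 40–55 | 10% | 50% | 24.9 | 36.3 | 44.1 | 47.5 |
| 24–36 | 0% | 95% | 6.8 | 6.8 | 30.0 | 30.0 |
| 24–36 | 0% | 58% | 23.2 | 24.3 | about 30 | 30.0 |

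At the other extreme, a large-sample run with 10% events, 40–55 months and no dropout gives 46.7 against 47.5, so the definition is nearly harmless there.

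**Step 4: what start-to-cut-off misses.** Without dropout it agrees with reverse Kaplan-Meier, apart from the 99% row, where only about 1 of 124 patients is censored. With 10% dropout per year it stays at 47.5 while the median time patients were actually observable is 44.0, an overstatement of 47.5 − 44.0 = 3.5 months.

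**The case against.** The strongest reply is that the larger number is already in the SAP. Start-to-cut-off is tabulated beside the criticised item, both formulas are printed, and in any no-dropout illustration reverse Kaplan-Meier gains almost nothing over it. This stands. A reader might infer that the SAP has no usable measure of follow-up; it does have one, for potential follow-up.

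Second, loss of observation is reported elsewhere. Censoring reasons are summarised for PFS and OS, SAP 4.6.1 separates withdrawal, loss to follow-up and lapsed assessments using an 18-week threshold, and SAP 2.5 tabulates disposition. These help a reader judge maturity, but counts of reasons are not a duration, so the gap remains.

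Third, reverse Kaplan-Meier is not clean for PFS. Table 2-1 censors PFS at the last adequate scan after new anticancer therapy or two or more missing assessments, even if progression or death is later known, and the reversed estimate would treat those dates as the end of follow-up. It may also rest on few patients: in the PFS example of Step 2 about 15% are censored, roughly 0.15 × 124 ≈ 19. This is a fair limit and calls for a footnote.

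Fourth, no test, estimate or decision changes. That is correct.

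**Conclusion.** The point holds as a weakness in descriptive reporting, of minor importance. The identity with the PFS or OS analysis time follows from the SAP's own definitions and needs no assumption. Its size does: it depends on the event fraction, potential follow-up and dropout, none of which the documents give.

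The effect is largest where events are common, which is plausible for PFS at the final analysis. In the assumed settings with most patients having events, the labelled median tracks the endpoint median, falling somewhat below it when there is dropout. For OS the effect is small if about half or fewer have died and dropout is low (41.7 against 47.5 months at 48% events). With 10% dropout per year it is not small even at 50% events (24.9 against 44.1).

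Three stronger readings are not supported:

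- A reader might infer that the PFS or OS results, or the ORR test, are biased. They do not use this variable.
- A reader might infer that the maturity of DOR is misreported. The definition covers PFS and OS only.
- A reader might take the 75% deaths trigger to mean that at least 75% had died by 22 January 2018. It is one of several alternatives in Protocol 4.3, and the SAP ties the cut-off only to the last patient's last visit. The trigger shows that a high event fraction is plausible, no more.

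**What to change.** In SAP 2.8.1, Duration of Follow-up and Gap Analyses:

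- Keep start-to-cut-off and label it potential follow-up.
- Report follow-up for OS, and for PFS by investigator and by BIRC, as the reverse Kaplan-Meier estimate: events treated as censored and censorings as events, with median, quartiles and 95% CI.
- Relabel the existing second item as observed PFS/OS time, or drop it.
- Footnote that for PFS, censoring for new anticancer therapy or for two or more missing assessments counts as the end of follow-up. Give the number of censored patients, and show the estimate beside the censoring reasons.

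The cost is a sentence or two of SAP text. The PROC LIFETEST call in SAP 4.6.3 serves with the censoring value changed from 1 to 0 and the alpha settings changed from 0.1 to 0.05, since the example is written for 90% intervals. No new data are needed. The remaining downside is the imprecision of the PFS estimate when few patients are censored.

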### 2.8.2 Safety

All safety analyses will be performed based on the Safety Set.

#### Baseline

Baseline is the result of an investigation describing the "true" uninfluenced state of the patient. The last available assessment before or on the start date of study drug is defined as "baseline" value or "baseline" assessment. If an assessment is planned to be performed prior to the first dose of study drug in the protocol and the assessment is performed on the same day as the first administration of study drug, it will be assumed that it was performed prior to study drug administration, if assessment time point is not collected or is missing. If assessment time points are collected, the observed time point will be used to determine pre-dose on study day 1 for baseline calculation. Unscheduled assessments will be used in the determination of baseline. See [Section 4.7.2](#) for further details on derivation of baseline for laboratory data and ECGs.

Patients who start treatment and discontinue from the study on the same day may have 2 different sets of data collected on study day 1, one being reported to the cycle 1 day 1 visit, the other reported to the end of treatment (EOT) visit. Data reported at the EOT visit are not eligible for baseline selection.

#### Grouping for the analyses

The overall observation period will be divided into three mutually exclusive segments:

- Pre-treatment period: from day of patient's informed consent to the day before first dose of study drug
- On-treatment period:

- o For discontinued patients, from day of first dose of study drug to 30 days after last dose of study drug
- o For ongoing patients, from day of first dose of study drug to the data cut-off date
- Post-treatment period: starting at day 31 after last dose of study drug

The safety summary tables will include only assessments collected no later than 30 days after study drug discontinuation and assessments prior to the data cut-off date for on-going patients, unless otherwise specified.

For select items, shift tables or change from baseline summaries generated for laboratory, ECG, vital signs and change score generation may use data from pre-treatment period for baseline calculations.

All data, regardless of observation period, will be listed and assessments collected in the pre-treatment and post-treatment period will be flagged in all table listings.

### **Adverse Events (AEs)**

AEs will be coded using the MedDRA 20.1 corresponding to the latest version available prior to planned date of clinical database lock (in case, the setting is changed, SAP will need to be amended) and will be graded using Common Terminology Criteria for Adverse Events (CTCAE) version 4.03. If CTCAE grading does not exist for an AE, grades 1, 2, 3, or 4 corresponding to severity of mild, moderate, severe, and life-threatening, respectively, will be used. CTCAE grade 5 (death) will not be used in this study; rather, this information will be collected on table "End of Treatment Phase completion", "Study Phase Completion" or "Death" eCRF pages.

All AE summaries will be summarized (frequency counts and percentages) by system organ class and/or preferred term, and maximum severity grades, except where otherwise noted. A patient with multiple CTC grades for an AE will be summarized under the maximum CTC grade recorded for the event.

The following AE summaries will be produced:

- AEs regardless of study drug relationship
- AEs suspected to be study drug related
- On-treatment deaths, by primary system organ class and preferred term
- SAEs regardless of study drug relationship
- SAEs suspected to be study drug related
- AEs leading to discontinuation of study drug
- AEs requiring dose adjustment
- AEs requiring study drug interruption
- AEs requiring dose adjustment or study drug interruption
- AEs requiring significant additional therapy

## **Adverse events of special interest**

Adverse events of special interest (AESIs) are defined as AEs within the following categories/groupings of preferred terms:

- Hepatotoxicity
- Interstitial Lung disease/Pneumonitis
- QT interval prolongation
- Bradycardia
- Hyperglycemia
- Gastrointestinal toxicity (nausea, vomiting and diarrhea)
- Pancreatitis (including lipase and amylase elevations)

The AESI definitions will be based on the electronic case review strategy (eCRS) for **LDK378** program based on MedDRA 20.1-

In case, the setting is changed, SAP will need to be amended.

These AESIs will be summarized for each grouping, by preferred term, as follows:

- All AESIs
- CTC grade 3/4 AESIs
- AESIs suspected to be study drug related
- CTC grade 3/4 AESIs suspected to be study drug related
- Serious AESIs
- AESIs leading to study drug discontinuation
- AESIs requiring dose adjustment
- AESIs requiring study drug interruption
- AESIs leading to dose adjustment or study drug interruption

## **Laboratory data**

For laboratory data assessments, data from all sources (central and local laboratories) will be combined. The summaries will include all laboratory assessments collected no later than 30 days after study drug discontinuation. All laboratory assessments will be listed and those collected later than 30 days after study drug discontinuation will be flagged in the listings.

Laboratory data will be classified (by Novartis Oncology CORR) into CTC grades according to the NCI CTCAE v4.03. For all reports, CTC grade is always obtained on the converted

measurement in SI unit. A severity grade of 0 will be assigned when the value is within normal limits. Grade 5 will not be used.

The following summaries will be produced for the hematology and biochemistry laboratory data (by laboratory parameter):

- Shift tables using CTC grades to compare baseline to the worst post-baseline value for laboratory parameters with CTC grades
- Shift tables using low, normal, high (as well as low and high combined) classifications to compare baseline to the worst post-baseline value for laboratory parameters where CTC grades are not defined.

The following lab parameters will be summarized:

- Hematology: absolute lymphocytes (decreased), absolute neutrophils (decreased), hemoglobin (anemia) (decreased), WBC (decreased); platelet counts (decreased)
- Biochemistry: alkaline phosphatase (APL) (increased), SGPT (ALT) (increased), SGOT (AST) (increased), total bilirubin (increased), amylase (increased), potassium (hyper and hypo), sodium (hyper and hypo), creatinine (increased), glucose (hyper and hypo), phosphate (hypo)

The following laboratory parameters will be presented in listings and will not be summarized: absolute basophils, absolute eosinophils, absolute monocytes, RBC, albumin, calcium, magnesium, creatinine clearance, direct bilirubin, blood urea nitrogen (BUN) or urea, GGT, urinalysis macroscopic panel (dipstick) (bilirubin, blood, glucose, ketones, WBC, pH, protein, specific gravity), Urinalysis Microscopic panel (RBC, WBC casts), Hormones (males only) Testosterone, LH, FSH, sex hormone binding globulin (SHBG), coagulation INR, prothrombin time (PT) or Quick Test.

The following listings will be produced for the laboratory data for all laboratory parameters where CTC grades are defined:

- Listing of patients with laboratory abnormalities of CTC grade 3 or 4
- Listing of all laboratory data with values flagged to show the corresponding CTC grades and the classifications relative to the laboratory reference ranges.

Liver function tests (LFTs) of interest for LDK378 are total bilirubin (TBIL), ALT, AST and ALP. In what follows, AT refers to ALT or AST values. LFTs will be summarized as follows:

- Shift tables of baseline vs. worst post-baseline-on-treatment values for the categories:
  - TBIL  $\geq 2 \times \text{ULN}$ , TBIL  $> 2 \times \text{ULN}$  and missing TBIL
  - ALT  $\geq 3 \times \text{ULN}$ , ALT  $> 3 \times \text{ULN}$  and missing ALT
  - AST  $\geq 3 \times \text{ULN}$ , AST  $> 3 \times \text{ULN}$  and missing AST
  - ALP  $\geq 2 \times \text{ULN}$ , ALP  $> 2 \times \text{ULN}$  and missing ALP
- Frequency counts and percentages of patients with worst post-baseline-on-treatment values in the categories:
  - ALT  $> 3 \times \text{ULN}$ , ALT  $> 5 \times \text{ULN}$ , ALT  $> 10 \times \text{ULN}$ , ALT  $> 20 \times \text{ULN}$
  - AST  $> 3 \times \text{ULN}$ , AST  $> 5 \times \text{ULN}$ , AST  $> 10 \times \text{ULN}$ , AST  $> 20 \times \text{ULN}$
  - AT  $> 3 \times \text{ULN}$ , AT  $> 5 \times \text{ULN}$ , AT  $> 10 \times \text{ULN}$ , AT  $> 20 \times \text{ULN}$

- o TBILI > 2xULN
- o Concmtent ALT > 3xULN and TBILI > 2xULN
- o Concmtent AST > 3xULN and TBILI > 2xULN
- o Concmtent AT > 3xULN and TBILI > 2xULN
- o Concmtent AT > 3xULN and TBILI > 2xULN and ALP > 1.5xULN
- o Concmtent AT > 3xULN and TBILI > 2xULN and ALP >= 2xULN

Concmtent measurements are those occurring on the same date.

In addition, a listing of all TBILI, ALT, AST and ALP values for patients with a post-baseline TBILI > 2xULN, ALT > 3xULN or AST > 3xULN will be provided.

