7.2.2.5 Laboratory evaluations

Central laboratories will be used for the analysis of scheduled hematology, biochemistry and other blood specimens collected as part as safety monitoring. All unscheduled blood testing will be performed locally. Dipstick urinalysis will be performed locally, except in the case of any out of range parameter on scheduled local urine analysis, when a urine sample will be sent to central laboratory for further analysis. Details on the collection, shipment of blood, urine and tumor samples and reporting of results by the central laboratory are provided to investigators in a separate [\[Laboratory Manual\]](#). The time windows granted for laboratory evaluations are identical to the corresponding visit time windows for each visit (refer to [Section 7.1](#)).

Laboratory values obtained at the screening visit will be used to assess eligibility to meet inclusion criteria 7. In addition, eligible patients must have baseline laboratory assessments performed on Cycle 1 Day 1 / Run-in Day 1 or within 24 hours prior to dosing. The results of centrally-analyzed laboratory assessments performed at Cycle 1 Day 1 do not need to be received by the site prior to initiation of dosing.

[figure not shown]

Table 7-3 Clinical laboratory parameters collection plan

Test Category	Test Name
Hematology	Hemoglobin, platelets, white blood cells (WBC), red blood cells (RBC), differential (basophils, eosinophils, lymphocytes, monocytes, neutrophils [% or absolute])
Blood Chemistry	Albumin, ALT, AST, calcium (at screening calcium corrected for albumin), creatinine, creatinine clearance, total bilirubin, direct bilirubin (only if total bilirubin is \geq grade 2), blood urea nitrogen (BUN) or urea, magnesium, potassium, sodium, fasting glucose, phosphate (inorganic phosphorus), alkaline phosphatase, amylase, GGT, lipase
Urinalysis	Macroscopic panel (dipstick) (bilirubin, blood, glucose, ketones, WBC, pH, protein, specific gravity) Microscopic panel (RBC, WBC, casts)
Hormones (males only)	Testosterone, LH, FSH, sex hormone binding globulin (SHBG)
Coagulation	INR and pro-thrombin time (PT) or Quick Test

Details on the collections, shipment of samples and reporting of results by the central laboratory are provided to investigators in the [Laboratory Manual].

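### Lipase is the one collected laboratory test that the SAP neither summarises nor names as listing-only, so no summary of measured lipase values is planned

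*SAP*

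**What the plan says.** SAP 2.8.2, Laboratory data, plans shift tables from baseline to worst post-baseline value and then names the tests they cover. The biochemistry names include "total bilirubin (increased), amylase (increased), potassium (hyper and hypo" but not lipase. A second group opens with "The following laboratory parameters will be presented in listings and will not be summarized" and includes GGT, albumin, calcium, magnesium and direct bilirubin. Lipase is not there either.

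Two general rules in the same section still reach lipase. One is "All laboratory assessments will be listed and those collected later than 30 days after study drug discontinuation will be flagged in the listings". The other is "The following listings will be produced for the laboratory data for all laboratory parameters where CTC grades are defined", whose first item is "Listing of patients with laboratory abnormalities of CTC grade 3 or 4".

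On adverse events, the SAP defines the special-interest category "Pancreatitis (including lipase and amylase elevations" and says "These AESIs will be summarized for each grouping, by preferred term, as follows". The tables that follow include grade 3/4 events and events leading to dose adjustment or interruption.

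In the protocol, the blood chemistry row of Table 7-3 ends with "alkaline phosphatase, amylase, GGT, lipase". Table 6-3 grades lipase and attaches a dose interruption and reduction to grade 3 or higher without symptoms. Section 10.5.3.3 plans CTCAE shift tables for hematology and biochemistry and does not exempt lipase.

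**The concern.** Lipase elevation is an identified risk of this drug. Amendment 3 was issued partly because of pancreatic enzyme elevations, and it added lipase to the laboratory collection plan. A final report written to this SAP would tabulate measured grades for amylase and not for lipase. The SAP does not say that this was intended.

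At stake is whether the report can state how many tested patients reached each lipase grade, and out of how many. A by-patient listing gives neither a rate nor a denominator. Adverse event tables give a rate, but one that depends on what investigators chose to report or were required to report.

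**Working it through.** This is mainly a comparison of texts, with one line of arithmetic for scale.

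**1. Is lipase the only gap?** Protocol Table 7-3 names 18 blood chemistry tests. Sorting them by SAP 2.8.2:
- Summarised (10): alkaline phosphatase, ALT, AST, total bilirubin, amylase, potassium, sodium, creatinine, glucose, phosphate.
- Listed only (7): albumin, calcium, magnesium, creatinine clearance, direct bilirubin, BUN or urea, GGT.
- Neither (1): lipase.

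10 + 7 + 1 = 18. The hematology, urinalysis, hormone and coagulation tests of Table 7-3 are all placed in one group or the other. A single gap in an otherwise complete division looks like an oversight, though that is an inference.

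**2. Is the departure declared?** SAP Table 3-1 lists changes to protocol-specified analyses. Its laboratory entry deletes the frequency table of newly occurring grade 3 or 4 values, on the ground that the shift table carries similar information. For lipase no shift table is named, so that reason does not apply. No other entry concerns lipase.

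**3. What do the adverse event tables cover?** Protocol 8.1.2.1 makes a laboratory abnormality an adverse event when the protocol requires a dose hold for it. Table 6-3 requires a hold for asymptomatic lipase of grade 3 or higher, so such values should reach the adverse event tables. Three things remain outside them:
- Grades 1 and 2 leave the dose unchanged in Table 6-3. They become adverse events only if they meet another criterion in protocol 8.1.1.
- Protocol 8.1.2.1 does not require separate recording of a result that corresponds to a sign or symptom of an event already reported. Lipase in a patient with reported pancreatitis may therefore have no term of its own.
- The percentages use the Safety Set, so patients never tested for lipase stay in the denominator. With x cases, N treated and m tested, the adverse event table shows x/N, which is m/N times the proportion among those tested. If half of N had been tested (an assumption; the documents give no figure), the percentage shown would be half of the percentage among those tested.

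**4. How late did collection start?** According to the protocol's Amendment 3 summary, recruitment was complete and 124 patients had been treated when lipase was added to Table 7-3. Scheduled baseline lipase may therefore exist for few or no patients. The documents do not say how many unscheduled or local values exist.

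**5. Scale.** Protocol 1.2.1.2.1 gives 5.1% grade 3-4 lipase increase among 255 patients at 750 mg in the earlier study. The matching count is 13, since 13/255 = 5.1% while 12/255 = 4.7% and 14/255 = 5.5%. If that rate held here, 124 × 13/255 = 6.3 patients. The chance of at least one such patient would be 1 − (242/255)^124 = 0.998. This is an adverse event rate, so it indicates how often the issue arises. It does not count cases that the plan would lose.

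**The case against.** A reader might infer that the grade 3/4 lipase rate will go untabulated, or that lipase will not be reported at all. The documents support neither. The SAP tabulates adverse events by preferred term and maximum grade, has a separate grade 3/4 table for special-interest events, and lists every laboratory assessment. Grade 3 or higher lipase that triggers a hold is a reportable adverse event under the protocol. The roughly 6 patients above are the kind of case those tables will show.

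A second objection is that a baseline-to-worst shift table could be nearly empty, because lipase entered the schedule after all patients had started treatment. That may be why only amylase was named, although the SAP does not say so. This objection stands against a shift table as the main display. It does not stand against a count of worst post-baseline grade among those tested; late collection makes a stated number tested more useful.

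A third is that the SAP also leaves GGT, albumin, calcium and magnesium without summaries. That is true, but for those tests it says so explicitly. For lipase it is silent, and lipase is the one tied to a special-interest category.

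**Conclusion.** The point holds in a narrow form. No summary based on measured lipase values is planned, and this is an undeclared departure from protocol 10.5.3.3. The reason given in Table 3-1 for dropping the grade 3/4 frequency table does not cover lipase. The adverse event tables are a partial substitute: they rely on investigator reporting, do not capture grades 1 and 2 systematically, and do not show how many patients were tested.

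The gap is minor. It does not touch the primary endpoint or any error rate. The figure of about 6 of 124 assumes that the earlier study's adverse event rate carries over, and is for scale only. How complete the lipase data are cannot be judged from the documents.

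**What to change.** In SAP 2.8.2, add lipase (increased) to the summarised biochemistry parameters, displayed as follows:
- Counts and percentages by worst post-baseline CTC grade, with the number of patients having any post-baseline lipase value as denominator.
- A row for patients whose baseline value is missing, and the baseline-to-worst shift only for patients who have a baseline value.
- A footnote stating that scheduled lipase collection began with Amendment 3, with the numbers having a baseline and a post-baseline value.

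If leaving lipase out was deliberate, say so in Table 3-1 and give the reason.

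The cost is one more parameter in an existing table. The drawback is an incomplete denominator: patients with lipase results may differ from those without, so the percentages describe tested patients and should be labelled that way.
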